# Follow-Up F-AV-1451 PET Imaging Visit:

Subjects will have a follow-up F-AV-1451 PET scan at 12 (+/- 3) months following the initial F-AV-1451 scan.

• A physician must see the subject prior to administration of F-AV-1451 Injection to determine if they are still suitable to undergo the scan;

- Vital signs will be taken (pulse rate, respiratory rate, supine blood pressure) at the following time points:
  - ➤ Immediately prior to administration of F-AV-1451 Injection (Weight will also be collected);
  - After completion of the 30-minute PET scan prior to discharge;
- Subjects will receive a single IV bolus injection target dose of 240 MBq +/-10%) of F-AV-1451 Injection followed by a saline flush;
- A 5-minute brain scan (1 frame of 5 minute duration) will begin immediately following the administration of F-AV-1451 (however if there are logistical or technical reasons this scan cannot obtained, it will not be a protocol violation);
- At approximately 75 minutes following injection, a continuous 30-minute brain scan (6 frames of 5 minute duration) will begin;
- The injection site will be observed for excessive inflammation or damage to the surrounding tissue where the dose was injected;
- Adverse events will be continuously monitored during the F-AV-1451
  PET imaging visit. Subjects who experience an adverse event will not be
  discharged from the imaging center until the event has resolved or
  stabilized;
- A physician will see the subject prior to discharge from the imaging center to evaluate the subject's readiness for discharge; and
- A follow-up phone call to the subject, or designated decision maker, will be conducted within 2 or 3 business days of the imaging day, but not before 48 hours post-injection, to confirm subject well-being and to collect information about any new adverse events. If both of these days are not business days, the follow-up phone call can occur the following business day.

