## 7.7.2 Adverse Event Definitions

#### Adverse Events

An adverse event is any undesirable experience occurring to a subject during a clinical trial, whether or not considered related to the study drug.

For reporting purposes, Avid will distinguish among pre-existing conditions, trial-emergent adverse events and treatment-emergent adverse events.

Pre-existing conditions (i.e., undesirable experiences, signs or symptoms that begin prior to the Screening Visit) will be recorded on the medical history and/or physical exam eCRF pages. During the study, site personnel will record any change in the condition(s) and occurrence and nature of any AEs. Signs and symptoms that are believed to be due to the pre-existing condition under study (started prior to dose of study medication) do not have to be recorded in the AEs section of the eCRF, unless there is an increase in frequency and severity. Additionally, signs or symptoms or changes in pre-exisiting conditions that occur outside the trial defined adverse event reporting period will be recorded in medical history.

An adverse event is any untoward medical occurrence associated with the use of a drug in humans, whether or not considered drug related. For the purposes of this study, untoward medical occurrences will be considered associated with the use of F-AV-1451, and thus be reported as adverse events, if they occur within 48 hours after administration of F-AV-1451. Adverse events associated with the use of F-AV-1451 will be recorded as treatment emergent relative to the respective drug. Adverse experiences that occur after administration of F-AV-1451 but outside the 48 hour reporting window will not be reported unless the investigator believes they are attributable to the drug.

In order to capture possible adverse effects of trial participation, trial-emergent adverse events will also be reported as any untoward medical occurrences occurring, during the study period but not during the 48 hour window following the administration of F-AV-1451. For the purpose of trial-emergent adverse events, the study period will be defined as beginning with the signing of consent and ending immediately before the administration of F-AV-1451.

The end of study for the purpose of adverse event reporting is defined as 48 hours after the administration of F-AV-1451.

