3.1.3 Flortaucipir PET Imaging Visits

3.1.3.1 Dosage and Administration

All subjects received a single IV bolus administration of approximately 240 MBq +/- 10% of flortaucipir injection at both the initial and follow-up flortaucipir imaging visit.

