5.3 SAFETY ASSESSMENTS

5.3.1 Adverse Events

An adverse event (AE) is any undesirable experience occurring to a subject during a clinical trial, whether or not considered related to the study drug. AEs are classed by severity and seriousness.

Treatment-emergent adverse events (TEAE) are any untoward medical occurrences associated with the use of a drug in humans, whether or not considered drug related. For the purposes of this study, untoward medical occurrences will be considered associated with the use of flortaucipir, and thus be reported as TEAEs if they occur within 48 hours after administration of the PET tracer. The end of study for the purpose of AE reporting is defined as 48 hours after the administration of flortaucipir injection.

The investigator's verbatim term of both serious and non-AEs will be mapped to system organ class (SOC) and preferred terms using the Medical Dictionary for Regulatory Activities (MedDRA) Version 17.0.

Severity is classified as mild/moderate/severe (increasing severity). If a subject reports a TEAE more than once within that SOC/preferred term (PT), the TEAE with the worst case severity will be used in the corresponding severity summaries.

Serious AEs (SAEs) are events that result in one of the following outcomes or constitute one of the following events:

- Death
- Initial or prolonged hospitalization (other than that required by protocol; "social hospitalization" or any hospitalization for non-medical reasons does not constitute an SAE)
- A life-threatening experience (that is, immediate risk of dying)
- Persistent or significant disability/incapacity
- Congenital anomaly/birth defect
- Considered significant by the investigator for any other reason

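### The SAP limits every adverse event table and its only adverse event listing to onset within 48 hours of an injection, so dated events that the protocol records outside that window have no planned adverse event output

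*Protocol*

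**What the plan says.** **Two injections.** Protocol 7.1.3 schedules a follow-up "PET scan at 12 (+/- 3) months following the initial" scan, and SAP 3.1.3.1 describes a flortaucipir "injection at both the initial and follow-up flortaucipir imaging visit".

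**What the protocol has recorded.** Events within 48 hours of dosing are treatment-emergent (7.7.2). Later events "outside the 48 hour reporting window will not be reported unless the investigator believes they are attributable to the drug". Under the same section, "trial-emergent adverse events will also be reported as any untoward medical occurrences occurring, during the study period", apart from the 48-hour window; for that purpose "the study period will be defined as beginning with the signing of consent and ending immediately before the administration of" the tracer. It then sets the end of reporting: "The end of study for the purpose of adverse event reporting is defined as 48 hours after the administration of" the tracer. Section 7.7.4 has serious events beyond 48 hours reported only if the investigator considers them related to drug or procedure, and serious events before dosing only if a procedure may have caused them. Section 7.7 asks the site to report the circumstances when an adverse event ends a patient's treatment, and gives no time limit of its own.

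**What the SAP outputs.** SAP 5.3.1 classes events as associated with the tracer, "and thus be reported as TEAEs if they occur within 48 hours after administration of the PET tracer", and adds: "The end of study for the purpose of AE reporting is defined as 48 hours after the administration of flortaucipir injection". Sections 7.5.3 (overall, SOC and PT tables, and the listing), 7.5.4 (severity), 7.5.5 (serious), 7.5.6 (discontinuation) and 7.5.7 (death) are all worded for treatment-emergent events. No other adverse event output is planned.

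**What the protocol promised.** Section 8.6 commits to summarizing every subject with a serious event or an adverse event discontinuation, and 8.1 to listing all eCRF data. Neither is limited to treatment-emergent events. SAP 4.2 says the planned analyses are unchanged and then names several exceptions, none about adverse events.

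**The concern.** The protocol's recording rules are wider than the SAP's outputs. An event can be one that the site must record and still have no table or listing to go into. The events that fall through include the most informative late ones, namely those the investigator attributes to the tracer and serious events related to drug or procedure.

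The schedule makes this more than theoretical. The phone call that asks about new adverse events is made no sooner than 48 hours after injection (protocol 7.1.3), so it can pick up events that began after the window closed. The SAP's own flow chart (Table 2) marks adverse event collection at screening, which precedes any injection, and at the MRI visit, which under SAP 3.1.2 may fall up to 6 months after the initial scan. Expanding the safety database is an exploratory objective of the study, and a report built strictly from the SAP would leave these events out of its adverse event section.

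**Working it through.** There is no sample size or power figure to reproduce. The check takes events of known onset through the protocol's recording rule and then through the SAP's output rule, with injection 1 at day 0 and, for illustration, injection 2 at day 365.

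| Event | Protocol | Treatment-emergent in SAP? | SAP adverse event table or listing | Possible trace elsewhere in SAP |
|---|---|---|---|---|
| Day 1 after either injection | Report (7.7.2) | Yes | Yes | n/a |
| After consent, 10 days before injection 1 | Report as trial-emergent (7.7.2) | No | None | None identified |
| 60 hours after injection, attributed to the drug | Report (7.7.2) | No: 60 − 48 = 12 hours too late | None | Phone-call listing (7.5.11) |
| Day 30, serious, related to drug or procedure | Report (7.7.4) | No | None | Disposition (7.2), if the subject withdrew |
| Between scans, leading to withdrawal | Circumstances reported (7.7); reason on CRF (5.5) | No | None | Disposition reason (7.2), not the event itself |
| Day 200, non-serious, unrelated | Unclear (7.7.2) | No | None | None identified |

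**Qualifier on dates.** SAP Appendix I can class an event with a missing or partial onset date as treatment-emergent. The result therefore applies to events whose known onset lies outside the windows.

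**The unclear row.** If the study period in 7.7.2 ends at injection 1, the day-200 event is not reported. If it ends at injection 2, one sentence has it reported as trial-emergent and another has it not reported. The text does not say which injection is meant. The first reading makes the exclusion of the 48-hour window redundant, while the second contradicts the express rule for late events. Protocol 10.7 adds that every adverse event during the trial is to be documented, related or not.

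**Calendar time.** One month = 365.25/12 = 30.4375 days.

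- Interval between injections: 9 × 30.4375 = 273.9 days; 12 × 30.4375 = 365.25; 15 × 30.4375 = 456.6.
- Time between injections outside the first window (interval − 2): 271.9, 363.25 and 454.6 days.
- Two windows as a share of the time from injection 1 to 48 hours after injection 2: 4/275.9 = 1.45%, 4/367.25 = 1.09%, 4/458.6 = 0.87%.
- A withdrawal that prevents the second scan must come before it, so only the first window can supply its event to the 7.5.6 table: 2/273.9 = 0.73%, 2/365.25 = 0.55%, 2/456.6 = 0.44% of the interval.

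These are shares of days, not of events.

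**The case against.** The strongest reply has five parts.

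1. **A short window suits a tracer.** The half-life is 109.77 minutes and clearance is rapid, so most illness months later in people over 60 would be background. This stands as a defence of the treatment-emergent definition. It does not explain why a late event that the investigator attributes to the drug, which the protocol asks for, has no output.

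2. **The events are not wholly lost.** Follow-up contact data are listed (SAP 7.5.11), discontinuation reasons are tabulated and disposition is listed (7.2), and Appendix I can bring poorly dated events into the tables. Protocol 7.7.2 also sends some out-of-period signs and symptoms to medical history, which is listed (SAP 7.3.2), although that sentence sits in the paragraph on pre-existing conditions and its reach is debatable. All of this narrows the point. None of it is an adverse event table or listing giving term, onset, seriousness and relationship.

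3. **The SAP is to be read with the protocol,** so the 8.1 and 8.6 commitments are not revoked. That is fair, and no intention to drop them should be inferred. But the SAP specifies no output that meets them.

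4. **Discontinuations.** Protocol 7.7 concerns an adverse event that ends treatment, and the reporting period for adverse events is set in 7.7.2. An unrelated event behind a withdrawal between scans may therefore not be on the adverse event page at all. This stands, and the point covers such events only where they were recorded.

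5. **The wording of 7.7.2 is mainly a drafting matter.** A reader might infer that the protocol leaves safety collection undefined, or that collection stops 48 hours after the first injection. The documents do not support either. Protocol 7.1.3 and the flow chart apply monitoring and the phone call to both visits, 7.7.4 gives one rule for serious events, 7.7.2 has an express rule for late events, and SAP Appendix I classifies against any injection. What remains unclear is the unrelated, non-serious event between scans.

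**Conclusion.** The gap in the SAP holds. Followed exactly, it leaves recorded adverse events with a known onset outside the 48-hour windows out of every adverse event table and the only adverse event listing. Four kinds are affected: trial-emergent events before dosing, later events attributed to the drug, later serious events related to drug or procedure, and recorded events leading to discontinuation between scans. The SAP therefore delivers less than protocol 8.1 and 8.6 promise, and section 4.2 does not say so.

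The size in events is unknown. The documents give no event rate, and unrelated events between scans may not have been recorded. A reader might infer from the 0.87% to 1.45% of days inside the windows that about 99% of the safety information is lost. That does not follow, because tracer-related events would be expected close to dosing and the remaining time would hold mostly background illness. The effect is confined to the safety objective, and no imaging result changes.

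The conclusion rests on the SAP outputs being produced as worded and on the site having recorded what protocol 7.7.2 and 7.7.4 require. The unnamed injection in 7.7.2 is a minor accompanying note.

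**What to change.** **In the SAP**

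- Add one listing of all recorded adverse events that are not treatment-emergent. Show onset relative to each injection and relationship to drug or procedure, and flag serious events, deaths and discontinuations.
- Report the number of subjects with any serious event or any adverse event discontinuation, regardless of onset. This supplies what protocol 8.6 promises.

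**In the study report**

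- State which rule the site applied to unrelated, non-serious events between scans, and that these may be incomplete. SAP 3.1.1 to 3.1.3 are in the past tense. If collection is complete, rewording protocol 7.7.2 would not recover events that were never recorded.

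**Cost.** One listing and one count from data already on the eCRF, with no new visit or assessment. The downside is some background illness in the listing that says little about a tracer; the relationship and onset columns let the reader separate it.

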# Serious Adverse Event (SAE)

An SAE is an AE that results in one of the following outcomes or constitutes one of the following events:

- Death;
- Initial or prolonged inpatient hospitalization (other than that required by protocol; "social hospitalization" or any hospitalization for non-medical reasons does not constitute an SAE);
- A life-threatening experience (that is, immediate risk of dying);
- Persistent or significant disability/incapacity;
- Congenital anomaly/birth defect;
- Considered significant by the investigator for any other reason.

Important medical events that may not result in death, be life-threatening, or require hospitalization may be considered serious adverse drug events when, based upon appropriate medical judgment, they may jeopardize the patient and may require medical or surgical intervention to prevent one of the outcomes listed in this definition.

# **Unexpected Adverse Event**

An unexpected adverse event is an adverse event not previously reported or an adverse event that occurs with specificity, severity or frequency that is not consistent with the current investigator's brochure.

## Relationship to Study Drug

Investigators will be instructed to report their assessment of the potential relatedness of each adverse event to protocol procedure or study drug. The assessment of the relationship of an adverse event to the administration of the study drug is a clinical decision based on all available information at the time of the completion of the eCRF.

#### Intensity/Severity of an Adverse Event

In addition to assessing the relationship of the administration of the study drug to adverse events, an assessment is required of the intensity (severity) of the event.

The following classifications should be used:

#### Mild:

A mild adverse event is an adverse event, usually transient in nature and generally not interfering with normal activities.

#### *Moderate*:

A moderate adverse event is an adverse event that is sufficiently discomforting to interfere with normal activities.

#### Severe:

A severe adverse event is an adverse event that incapacitates the subject and prevents normal activities. Note that a severe event is not necessarily a serious event. Nor must a serious event necessarily be severe.

#### 7.7.3 Adverse Event Documentation

All adverse events must be fully recorded on the adverse event eCRFs. Documentation must be supported by an entry in the subject file. Laboratory test, vital signs and ECG abnormalities considered by the Investigator to be clinically relevant should be reported on the adverse event eCRFs. Signs and symptoms of each AE should be described in detail (e.g., start and stop dates/time, severity/intensity, relationship to study drug, action taken, and outcome).

Adverse events and laboratory test abnormalities fulfilling the definition of a serious adverse event should, in addition, be reported on the Serious Adverse Event Reporting Form.

#### 7.7.4 Reporting of Serious Adverse Events

Study site personnel must alert Eli Lilly or its designee of any SAE within 24 hours of their awareness of the event via a sponsor-approved method. Alerts issued via telephone are to be immediately followed with official notification on study-specific SAE forms.

Serious adverse events occurring after a subject receive a dose of study drug will be collected until 48 hours after the dosing of the study drug, regardless of the investigator's opinion of causation. Therefore, SAEs that occur later than 48 hours after the dosing of the study drug are not required to be reported unless the investigator feels the events were related to either study drug or a protocol procedure.

If a patient experiences an SAE after signing informed consent, but prior to receiving study drug, the event will NOT be reported unless the investigator feels the event may have been caused by a protocol procedure. Previously planned (prior to signing the ICF) surgeries should not be reported as SAEs unless the underlying medical condition has worsened during the course of the

study.

#### 8. STATISTICAL ANALYSIS

#### 8.1 General Statistical Considerations

All statistical analyses will be performed using SAS® version 8.2 or higher.

The study data collected under AIBL protocol, such as but not limited to subjects' demographic and baseline characteristics, history taking, clinical assessments, neuropsychological evaluations, florbetapir (F) and MRI scan will be transferred to study investigator and study sponsor (Avid) for analysis purpose.

Data will be summarized using descriptive statistics (number of subjects [N], mean, standard deviation [SD], median, quartiles, minimum, and maximum) for continuous variables and using frequency count and percentage for discrete variables. The demographic and baseline characteristics data will be summarized for all subjects in the safety population according to clinical group. Safety data will be summarized for all patients. Subject listings of all data from the electronic case report forms (eCRFs) as well as any derived variables will be presented.

# 8.2 Sample size estimation

Due to the exploratory purpose of this study, the sample size was determined outside statistical consideration.

# 8.3 Image Analysis

All F-AV-1451 PET images obtained starting at 75 minutes post injection will be analyzed. The F-AV-1451 PET images will be spatially normalized to standard stereotactic atlas space using MNI brain atlas. The uptake in tau protein rich brain regions will be assessed with regions of interest (ROI, designed in MNI brain atlas) in terms for standard uptake value ratio (SUVR, normalized by cerebellar uptake). The spatially normalized images and the measured SUVR values will be used to accordingly for the following objectives.

Mean, standard deviation, minimum and maximum of the SUVR values for all groups will be calculated.

Exploratory analysis will include co-registration of MRI to F-AV-1451 PET images and partial volume correction of F-AV-1451 PET images using anatomical information from MRI data.

## 8.4 Primary objective analysis

Descriptive statistics will be applied to summarize the tau deposition as measured by F-AV-1451 uptake values by clinical enrollment groups. Box-and-Whiskers plots by clinical enrollment groups will be created to describe the tau deposition

distributions. ANOVA test will be applied to compare the tau deposition between subjects with objective cognitive impairment (MCI and AD) and subjects without objective cognitive impairment (healthy controls and subjects with SMC) at baseline, and at 12 months follow up visit. If the pre-requisites of ANOVA are not met then appropriate non parametric test such as Kruskal-Wallis test will be applied.

#### 8.6 Safety Analysis

Safety laboratory test results and vital signs measurements will be summarized by subject and by evaluation time point. Change from baseline (pre-dose time point) values will be determined and summarized. Subjects whose laboratory values are outside the pre-determined upper and lower limits of normal will be identified and tabulated.

Adverse events including injection site reactions will be summarized in terms of number and percentage of subjects experiencing an AE. The summary will be further broken down by system organ class (SOC) and preferred term using Medical Dictionary for Regulatory Activities (MedDRA) terms. Adverse events will also be presented by severity, relationship to study drug and seriousness. All subjects who experience SAEs or who discontinue due to AEs will be summarized.

